3.2.1.1 Age 12-24 years

- 3.2.1.1.a** Patient aged 12-17 years: has signed informed assent and their parent/legal guardian has signed informed consent for study participation.
- 3.2.1.1.b** Patient aged 18-24 years: has signed informed consent for study participation.
- 3.2.1.2** Receiving allogeneic or autologous HCT for treatment of malignancy or bone marrow failure syndrome at Seattle Cancer Care Alliance (Seattle Children's Hospital and Fred Hutchinson Cancer Research Center), Children's Hospital Los Angeles (CHLA), University of Alabama at Birmingham (UAB) or St. Jude Children's Research Hospital (SJCRH).
- 3.2.1.3** Within 4 weeks of their HCT date ("day zero") (if prior, their planned HCT date)
- 3.2.1.4** Patient able to speak in the English language
- 3.2.1.5** Patient able to read in the English or Spanish language
- 3.2.1.6** Cognitively able to participate in interactive interviews

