9.0 Procedures Involved

9.1 Enrollment. Once consent documents are signed and all questions addressed, the consenting RA or study staff will register the patient in the RedCap System. Randomization will not occur until after the baseline Resilience in Pediatric Cancer Assessment (RPCA) surveys are collected (see below). Site RAs will maintain original copies of all consent forms and fax/email copies to the coordinating center for secure storage and tracking purposes.

9.2 Randomization.
 As a quality control measure, a randomization log will be maintained at SCH to track the participant ID, stratum, randomized assignment, and date of randomization. Patients will be randomized only after completion of the baseline surveys and in a 1:1 ratio to receive usual, non-directive, supportive care without PRISM (“control” arm) or with PRISM (“experimental” arm). Randomization will be stratified by age (patients ages 12-17 versus ages 18-24 and site). Biostatisticians who will conduct data analysis will be blinded from the treatment group allocations. Throughout the screening period until allocation of the control or PRISM, participants will be assigned a screening number, according to the chronological order of screening. Once enrolled, the participant will be assigned a study ID.

9.3 Scheduling of study procedures with participants.

9.3.1 Baseline Survey Completion Upon enrollment, study staff will deliver the baseline survey in participant's preferred language (English or Spanish). For both English and Spanish, the study will first be offered by email via REDCap or via

REDCap on a study team iPad. Upon request, staff will offer paper-pencil versions and/or interview-based versions (interviews only available in English).

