Patient (and parent) reported outcomes (PROs) will be measured with the Resilience in Pediatric Cancer Assessment (RPCA), a comprehensive survey comprised of age-appropriate validated instruments (**Table 5**). The RPCA was designed with AYA and parent stakeholders to capture patient-reported outcomes associated with resilience resources.³⁰ We have successfully used it in several of our prior studies.^{29,30,90-92,99} The survey includes embedded validated instruments as well as standard demographics (age, sex, and race/ethnicity, education, income, number of children in the home).

The full RPCA survey will be administered to patients and parents at baseline, month 3 and month 6 (**Figure 3**). In order to optimize engagement, parents in both arms of the study will be asked to complete the abbreviated Resilience in Pediatric Cancer Assessment (aRPCA) at months 1, 2, 4, and 5. The aRPCA will assess only cost-consequences, as described below. In the rare case that a patient is their own money manager, AYA patients will be asked to complete cost-consequence questionnaires at each month in lieu of parents. RPCA and aRPCA surveys will be administered via REDCap or pencil-and-paper, depending on participant preference. If administered via REDCap, participants will be sent an email containing the survey link. Email language will include all text described in the IRB-approved template (see “PRISM BMT Survey letter – REDCAP”) though additional personalized text may be included to reflect participants’ specific needs. Paper-and-pencil surveys will be delivered in-person or via mail. If patients or parents specifically request to opt-out of aRPCA surveys (i.e., cost consequences assessments), study staff will no longer administer aRPCA surveys for the remainder of the study. In these cases, patients/parents will remain eligible to complete RPCA surveys.

For those on the non-intervention arm of the study, staff will schedule a “study check-in” visit to coordinate the aRPCA completion and thank families for their continued participation. If patients and parents have not completed any interval study questionnaires, we will still invite them to complete the 6 month questionnaire regardless of how many intermediate questionnaires they have completed. If patients and parents

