11.0 Data Analysis/Management

11.1 Overview

The primary statistical analyses will be intention-to-treat to avoid confounding by non-random participant attrition or crossover. Demographics, clinical characteristics, items within the RPCA, adherence data, and costing data will all be summarized at each time-point using descriptive statistics: frequencies and proportions for categorical variables, means and standard deviations for continuous variables, or median and interquartile range if distribution is skewed. All analyses will be adjusted for patient age and site, as randomization is stratified by age and site, as well as baseline characteristics clearly imbalanced between groups. Additional baseline characteristics we consider as potential confounders include sex, race, and primary language spoken at home.

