11.4 Analysis Plan

11.4.1 Primary Outcome (Anxiety and Depression [HADS scores]). Our primary outcome is AYA reported total HADS score at 6 months. Because the amount of change depends strongly on the initial score at baseline we will control for baseline score as a covariate in the regression. Regression models will be used to estimate mean-level differences and 95% confidence intervals comparing scores in the PRISM intervention to those in usual care. The total HADS score will be the outcome, and PRISM intervention indicator will be the predictor of interest. Baseline HADS score, age group, site and other unbalanced confounders will be covariates in the regression. With this model specification, the regression coefficient of PRISM indicator captures the difference in the average changes (from baseline to 6 months) for the HADS score between PRISM arm and usual care arm. Thus the primary hypothesis can be tested by applying the Wald t-test to the regression coefficient of PRISM indicator. The same analysis will be undertaken for the domain subscales of anxiety and depression (HADS-A and HADS-D subscale scores).

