11.4.2 Secondary Outcomes

11.4.2.1 AYA patient reported outcomes. The same analysis as above will be undertaken for the secondary outcomes of symptom burden, generic- and cancer-specific quality of life, hope, and resilience.

11.4.2.2 Cost per Quality Adjusted Life Year (QALY). We will use a cost-effectiveness framework to evaluate the overall value of PRISM.⁸¹ We anticipate that supportive care and PRISM will be cost-effective compared to supportive care alone. The main cost-analyses will determine the total, per-patient, 6-month costs of PRISM versus usual care. Using Quality-adjusted life years (QALYs) we will then estimate the incremental cost-effectiveness ratio (ICER)

Costs will be calculated with a micro-costing approach, multiplying resource use by unit costs.⁸⁰ Resource utilization will be valued through the Medical Expenditures Panel Survey^{125,126} and the Healthcare cost and utilization project,^{127,128} with additional information from the Federal Supply Schedule.^{78,79} For example, PRISM utilization will be calculated by estimated cost per visit category (e.g., in-person check-in with/without formal session), plus estimated costs of intervention delivery (including facilities and overhead). We will add a fixed \$50 per patient cost for caseload supervision and information support, consistent with prior analyses of collaborative psychosocial interventions.¹²⁹⁻¹³¹ Patient costs will be valued using opportunity cost methods and the proxy-good method in sensitivity analyses.¹³²

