We will calculate ICERs to provide information on the incremental cost for each additional unit of change in QALYs. Because the goal of cost-effectiveness analysis is to inform decisions about resource allocation and assess intervention value, traditional hypothesis testing is rarely utilized.⁸⁰ Uncertainty in all ICER estimates will be quantified using non-parametric bootstrapping and calculation of a 95% confidence interval (CI) with Fieller's method.^{133,134} We will calculate QALYs with standard utility values (preference-based measures of quality of life ranging from 0 to 1, defined by the Health Utilities Index).¹⁰² Sensitivity analyses will calculate QALYs with assigned values for HADS scores (1.0 for no, 0.8 for mild, and 0.6 for severe anxiety or depression) as described previously.¹³⁵⁻¹³⁷ The rationale for this dual approach is that preference-based scoring in pediatrics has limitations because rapid developmental changes make it difficult to identify health attributes (and hence, utility values) relevant to all age groups.¹³⁸

11.4.3 Parent Outcomes. The same analysis as above (primary outcome and Aim 2A) will be undertaken for the parent outcomes.

11.4.4 Patient Outcome Trajectories. We will use descriptive statistics to summarize patient-reported outcomes in each study arm at enrollment, 3 months and 6 months. We will plot individual patient trajectories across all time-points for each outcome measure and attempt to identify trajectory patterns (e.g., stable vs. temporary or sustained improvement or deterioration) within study groups. We will also plot outcome summaries across time by study group to assess between-

group differences in overall trajectories and variability.

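### No baseline-HUI adjustment is specified for the incremental QALY, although the plan adjusts the other patient-reported and parent outcomes for their baseline score

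*Combined protocol and SAP*

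**What the plan says.** All references are to the combined protocol and SAP.

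- **11.4.1 (primary outcome)** puts the baseline score in the model as a matter of course and gives the reason: "Because the amount of change depends strongly on the initial score at baseline we will control for baseline score as a covariate".
- **11.4.2.1 (other patient outcomes)** carries the model over: "The same analysis as above will be undertaken for the secondary outcomes of symptom burden", followed by quality of life, hope and resilience. HUI and QALYs are not in the list.
- **11.4.3 (parents)** does likewise: "The same analysis as above (primary outcome and Aim 2A) will be undertaken for the parent outcomes".
- **11.4.2.2 (QALY)** sits between these two. It says "We will calculate QALYs with standard utility values (preference-based measures of quality of life ranging from 0 to 1", names the HUI as the source, and provides for ICERs with non-parametric bootstrapping and a Fieller interval. It gives no rule for turning utilities into QALYs, no regression and no baseline covariate.
- **11.1 (overview)** adjusts every analysis for age and site, "as well as baseline characteristics clearly imbalanced between groups". The potential confounders it names are sex, race and home language, not HUI.
- **The covariate will be on file.** On timing, 9.2 says "Patients will be randomized only after completion of the baseline surveys". On content, 9.7 says "The full RPCA survey will be administered to patients and parents at baseline, month 3 and month 6", and 9.8.2.1 places HUI in the full survey.

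**The concern.** The QALY difference is the denominator of the ICER in secondary aim 1.4.2. The plan's own reason for baseline adjustment applies at least as directly to a QALY as to HADS. If the QALY is an area under the utility curve, the baseline utility is one of the terms summed, so baseline noise enters the QALY difference arithmetically as well as through correlation with later scores.

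Two things are at stake. The interval for the QALY difference would be wider than the collected data allow. And whether baseline HUI is a covariate would rest on a judgement of imbalance, with no stated criterion, made after the data are seen. Costs and the primary HADS analysis are not touched.

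**Working it through.** **The plan's own figures.** The documents give no HUI SD, between-visit correlation, QALY formula or QALY power, so no QALY figure can be reproduced. The sample size used below does reproduce from 11.2: n per arm = 2 x (1.96 + 0.84)^2 x 6.2^2 / 4.2^2 = 34.2, rounded up to 35.

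**Inputs.** From the plan: 35 evaluable per arm (11.2), HUI at months 0, 3 and 6 (9.7, 9.8.2.1) and $150,000 per QALY (1.4.2). Assumed: the trapezoid rule, equal HUI SD at the three visits, the correlations, an HUI SD of 0.2 where QALY units are needed, and cost SDs.

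**Formula.** With U0, U3 and U6 the HUI at each visit and time in years,

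Q = 0.25 x (U0 + U3)/2 + 0.25 x (U3 + U6)/2 = 0.125 U0 + 0.25 U3 + 0.125 U6.

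In units of the HUI variance:

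- Var(Q) = 0.09375 + 0.0625 r03 + 0.03125 r06 + 0.0625 r36
- Cov(Q, U0) = 0.125 + 0.25 r03 + 0.125 r06
- adjusted variance = Var(Q) - Cov(Q, U0)^2

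At a common correlation of 0.5, Var(Q) = 0.1719 and Cov = 0.3125. The adjusted variance is 0.1719 - 0.0977 = 0.0742, and the SE ratio is sqrt(0.0742/0.1719) = 0.657, a cut of 34.3%. With equal SDs the percentage does not depend on the SD or on n.

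**Range.** The last column repeats the calculation with the baseline SD at half the later SD.

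| r03 / r06 / r36 | SE cut, equal SDs | SE cut, baseline SD halved |
|---|---|---|
| 0 / 0 / 0 | 8.7% | 2.4% |
| 0 / 0 / 0.5 | 6.5% | 1.7% |
| 0 / 0 / 0.7 | 5.9% | 1.6% |
| 0.2 / 0.1 / 0.5 | 13.4% | 6.7% |
| 0.3 / 0.1 / 0.5 | 16.8% | 9.5% |
| 0.3 / 0.3 / 0.3 | 22.6% | 14.4% |
| 0.5 / 0.5 / 0.5 | 34.3% | 26.3% |
| 0.7 / 0.7 / 0.7 | 48.9% | 42.2% |

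A simulation of 6,000 trials with 35 per arm, equal SDs, and age group and four sites in both models, gave cuts of 5.6% at 0/0/0.5, 34.8% at 0.5 and 48.2% at 0.7. Both estimators averaged about zero when the true effect was zero.

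**In QALY units (SD 0.2, 35 per arm, t = 1.995).** SE = 0.2 x sqrt(2 x variance / 35).

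- Correlation 0.5: SE 0.0198 to 0.0130; 95% half-width 0.040 to 0.026.
- 0/0/0.5: SE 0.0169 to 0.0158; half-width 0.034 to 0.032.

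**Net benefit at $150,000 per QALY.** With costs uncorrelated with QALYs, the per-patient variance is (cost SD)^2 + 150,000^2 x 0.04 x variance of Q. At correlation 0.5 the QALY term is 9 x 10^8 x 0.1719 = 1.547 x 10^8 unadjusted and 9 x 10^8 x 0.0742 = 0.668 x 10^8 adjusted.

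| Assumed cost SD | Per-patient SD, unadjusted to adjusted | SE cut |
|---|---|---|
| $10,000 | $15,959 to $12,915 | 19% |
| $20,000 | $23,552 to $21,605 | 8% |
| $50,000 | $51,524 to $50,664 | 1.7% |
| $100,000 | $100,770 to $100,333 | 0.4% |

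At 0.3/0.1/0.5 the four cuts are 9%, 4%, 0.8% and 0.2%.

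**Sensitivity to the QALY formula.** If the QALY were a gain over baseline, Q - 0.5 U0, the cuts would be 34% (0/0/0.5), 18% (0.5) and 10% (0.7). The pattern reverses, but the adjusted variance is the same as before, because subtracting a multiple of U0 changes nothing once U0 is a covariate. So the percentage gain depends on the formula, and the adjusted answer does not.

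**The case against.** **11.1 already allows it.** This is right as far as it goes. Age and site are covered for every analysis, and baseline HUI could enter, so a reader who infers that the plan rules out adjustment goes too far. But that entry is conditional. The plan did not rely on 11.1 for HADS; it named the baseline score separately. The same data-dependent rule also applies to other covariates in the primary model, so that part of the complaint is not peculiar to QALYs.

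**Randomization protects the estimate.** It does. A reader might infer that the ICER would be biased in one arm's favour. Nothing in the documents supports that: allocation is randomized 1:1, the unadjusted QALY difference is unbiased, and the direction of any change from adjustment cannot be known in advance.

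**The gain may be small.** This stands in three ways.

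- Baseline falls near transplant ("Within 4 weeks of their HCT date"), so it may predict later utility poorly.
- Under 9.8.2.1 a parent's proxy HUI replaces a missing patient HUI, so the rater can differ between visits, which could weaken the correlations.
- Section 11.2 itself describes costs as widely variable, and cost noise dilutes the gain in net benefit. The percentage for the QALY component must not be read as the percentage for the ICER.

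**Deaths.** A reader might also infer that the plan mishandles death in the QALY, since 11.7 lists death among causes of missing data and 14.2 censors participants who die. The documents do not support that. They do not say how death enters a QALY, 9.8.2.1 anchors utility 0 at death, and 14.2 concerns participation and survey follow-up, not valuation.

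**Conclusion.** The omission is real and limited to precision. Section 11.4.2.2 specifies no baseline-HUI adjustment for the incremental QALY, while the neighbouring sections always adjust for the baseline score.

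For the QALY component, the avoidable part of the SE is about 6-49% over baseline correlations of 0 to 0.7, given a trapezoid and equal SDs, or about 2-42% if the baseline SD is half the later SD. For net benefit at $150,000 per QALY, with correlation 0.5 and HUI SD 0.2, it is about 19% at a cost SD of $10,000, 8% at $20,000 and under 2% at $50,000 or more. The QALY formula, HUI SDs, correlations, cost SDs and zero cost-QALY correlation are all assumptions.

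The change is worth making because it costs nothing and settles the covariate before the data are seen. The cost-effectiveness conclusion is not shown to be at risk without it.

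**What to change.** In 11.4.2.2, before any analysis by arm:

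1. Define the QALY as the area under HUI at months 0, 3 and 6, and say whether HUI2 or HUI3 is scored (9.8.2.1 describes both).
2. Estimate the incremental QALY by regression on arm with baseline HUI, age group and site as prespecified covariates.
3. Refit that regression within each bootstrap replicate, so that the ICER interval carries the adjustment.

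An optional clarification, separate from this point, is to value utility as 0 from the date of death, in line with the anchor in 9.8.2.1.

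The cost is SAP wording and slightly more programming in the bootstrap. No new data are needed, since baseline HUI is collected before randomization. Sample size, costs and the primary analysis are unchanged.

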11.5 Exploratory Analyses

11.5.1 **Digitally (MEMS-cap) assessed medication adherence rates** will be defined as [(# events of MEMS cap opening/# events prescribed)] x 100. Days when oral GVHD medications were held by the prescriber (captured via medical record abstraction) will be removed from the denominator, whereas “missed doses” will be defined as those where no cap was opened on a day medication was prescribed. Adherence will be calculated on a monthly basis and summarized both monthly, and as a 3-month average.

11.5.2 We will calculate **incremental cost consequence ratios** (e.g., the cost for each unit of improvement in average HADS scores or adherence) using the same costing numerators as above with the HADS and adherence change as the denominator. These will be included not as a threshold for cost-effectiveness, but as part of a comprehensive evaluation of both costs and consequences of the intervention.

11.5.3 **To explore the contribution of different cost parameters to total healthcare costs**, we will analyze disaggregated costs (e.g., formal-, informal-, and non-healthcare sector costs) from a payer and societal perspective.^{78,139} A similar analysis will be completed from the societal perspective. An incremental analysis will estimate the arithmetic mean difference in costs between intervention and control patients using multivariable generalized linear analytic techniques to adjust for variability in outcomes based on baseline characteristics. Sensitivity analyses will model the potential range of cost impact based on variable fee-for-service and out-of-pocket expenses

To explore family experience scores, we will conduct descriptive analyses of categorical data. Comparisons will include standard hypothesis testing including chi-square tests for frequency data and Kruskal Wallis for non-parametric differences in distribution of responses.

11.5.4 **We will explore the relationship between biomedical variables and patient reported anxiety and depression** through a combination of paired and unpaired t-tests, chi-squared (or Fisher's exact) tests, and linear and logistics regression. DNE will be defined as the number of days from transplant to an absolute neutrophil count (ANC) of >500/mm³ for >3 days. Cumulative incidence and severity of Grade II-IV GVHD will be defined by the revised Seattle Criteria as documented by the patient's clinical provider. HRV will be measured in 24-hour increments using both time and frequency domain parameters as established by the international Cardiology task force guidelines. Means and standard deviations will be compared to published normative data in adolescents. CTRA scores will be divided into two groups (above and below the median). We will perform multivariable analyses, adjusting for age, sex, diagnosis, disease status at the time of transplant, conditioning intensity, and,

immunosuppressive medications/GVHD prophylaxis to examine the association between CTRA biology and HCT outcomes.

11.6 Additional analyses, confounders, and other considerations.

We will conduct interaction modeling and subgroup analyses to explore whether the effect of the intervention is modified by medical covariates, symptom distress, and/or adherence. The rationale for these subgroup analyses is grounded in prior findings suggesting symptoms, adherence, and overall well-being are associated.¹⁴⁰

We will conduct a thorough process evaluation that includes: (a) intervention fidelity; and, (b) satisfaction queries. Multiple comparisons are a concern since we are collecting multiple measures from patients and are interested in several hypotheses. We minimize this problem by specifying a limited number of main hypotheses for each aim. The Benjamini-Hochberg procedure will be used to control the False Discovery Rate criterion at $\alpha=0.05$ to correct for multiple testing in analyses that are not pre-specified.¹⁴¹ Likewise, in manuscripts and presentations, we will report the number of tests performed and interpret results within this context.

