Beginning 2 weeks following the date of discharge from initial HCT hospitalization and for the final duration of the remaining 6 months on study, participants will store prescriptions for their primary GVHD prophylaxis (typically either tacrolimus or cyclosporine), in study-dispensed MEMS bottles and caps. A patient supply kit containing a MEMS cap and bottle will be dispensed to all study participants by the institutional RA no more than 7-10 post discharge. The patient will receive instructions directing them to put their primary GVHD prescription into these bottles and to take their prescription using the MEMS medication bottle. The patient will be instructed that any additional refills of their GVHD prophylaxis required during the study period are also to be added to their MEMS medication bottle. When possible, the study RA will meet with families in person approximately 2 weeks post-discharge to verify new prescription has been dispensed in these bottles and to review procedures. A study coordinator will

contact study participants monthly by phone, email, text or in person to answer any questions or concern the patient may be having.

The following instructions will be included in the patient supply kit:

1. In the next 1 -2 days, please put your main GVHD prophylaxis medication into your MEMS medication bottle. If you are unsure what medicine this is, please check with your study team.
2. Once you have filled your bottle, before you take your next dose of your GVHD medication, please replace the regular cap with the MEMS TrackCap you received in your study kit.
3. All doses of your GVHD medication should be taken from the MEMS medication bottle with the MEMS TrackCap while you are on this study.
4. Please take your GVHD medication exactly as your doctor has ordered.
5. Open the medication bottle ONLY when it is time for you to take your GVHD medication.
6. Close the medication bottle right after taking the GVHD medication.

➤ To refill your GVHD medication while on this study, follow these instructions.

- Only refill your medication when you need to take a dose of your GVHD medication!
 - Open the old bottle and take out a dose of medication.
 - Refilled bottle with your GVHD medication using your prescription bottle from your pharmacy.
 - Replace the electronic Trackcap onto the newly refilled bottle of your GVHD medication.
 - Please do not refill or open your MEMS cap when you are not taking your medicine.

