9.6.2 Health care utilization. The Case Report Form (CRF, appendix) will capture the following variables through medical records and billing systems: (1) Intervention time: visit time related to case management and PRISM sessions; (2) mental health utilization: number, location, and duration of formal psychosocial clinician visits, psychological diagnoses, number of prescription psychiatric medications; and, (3) additional relevant utilization: number of supportive care medications (including acute and chronic pain medications and sleep-aids), number of and reason for unplanned hospital days, Emergency Department, outpatient clinic visits; resource use associated with additional health problems and diagnoses such as medical treatments and procedures, additional hospital services, distance between home and primary care facility (documented by home zip code), etc.

9.6.3 Additional covariates. RA's at each site will prospectively abstract the following clinical covariates from the medical record (using study-specific CRFs, appendix): the AYA's diagnosis, GVHD-directed treatments (and modifications), and treatment-intensity in the past month.⁹⁸ These variables were selected to capture relevant costs and based on prior evidence that AYA well-being and family psychosocial needs affect immediate psychosocial outcome metrics (e.g.,

psychological distress and quality of life).^{46,98} In addition, RAs at each site collecting biomarker data (i.e., heart rate variability and/or blood samples) will abstract additional clinical covariates to provide needed context as to the conditions under which the corresponding biologic data were collected. These data will only be collected for participants who consented to the HRV and/or CTRA optional components of the study. Sites collecting heart rate variability (HRV) data will abstract the following clinical information for participating patients: cardiac medications, diagnostic cardiac test data, and patient weight, height, and Body Mass Index (MBI). Sites collecting blood samples will abstract the following information for participating patients: date of conditioning chemotherapy and/or radiation start, transplant date, and blood test information.

9.7 Resilience in Pediatric Cancer Assessment (RPCA) Survey (both arms):

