13.6 Blood Samples

5 mL whole blood will be collected in a PaxGene (PreAnalytiX GmbH) blood tube at the time of a planned clinical blood draw. These biospecimens will be labeled with the subject's study ID only (no identifying information) and sent to the Seattle Children's Research Lab Services (RLS) Core (Seattle Children's Hospital, Seattle, WA) for storage. De-identified, batched blood samples will be shipped by RLS to the University of California Los Angeles (UCLA) Social Genomics Core Laboratory for analysis.

13.7 Data Collection Procedures/ Internal Site Monitoring plan:

The coordinating center will be responsible for systematic data collection, quality control, and data-management procedures including: (1) oversight of ongoing data collection; (2) rigorous training and ongoing monitoring of adherence to protocols; (3) regular review of questionnaire response rates and missing items to identify and correct problems; (4) verification of all data through computerized data entry systems restricting invalid/out-of-range responses; (5) at minimum monthly meetings and progress reports to provide feedback to study staff concerning difficulties and follow-up to ensure problems are resolved quickly, and (6) yearly on-site monitoring of participating sites.

13.7.1 Survey data:

To optimize collection, all participant surveys will be available by paper or online via the REDCap system, a secure HIPAA-compliant, high-quality data collection tool. The rationale for offering both paper-pencil and electronic versions is based on our prior experience where participants preferred the former,⁹² which in turn facilitated more complete data collection. To ensure primary outcome data, we will offer an abbreviated survey with only the HADS and HUI for those who do not complete all assessments or who request to drop out. To ensure data quality, a RA will review RPCA surveys within 72 hours of their completion for missing fields and call participants to clarify and query/complete individual missing items verbally.

13.7.2 MEMS caps:

One to two weeks following discharge from the initial HCT and the day after any subsequent hospitalizations, an RA will contact the family by phone to review the MEMS-cap system and, where relevant, confirm the MEMS-cap is being used. Where indicated, to identify obstacles and solutions to its use.

13.7.3 Medical record data:

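### The MEMS adherence rule drops only prescriber-held days, so readmission days with the oral drug still prescribed but not taken from the MEMS bottle would be scored as missed doses

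*Combined protocol and SAP*

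**What the plan says.** Section 11.5.1 states that the adherence rate "will be defined as [(# events of MEMS cap opening/# events prescribed)] x 100". It gives one exclusion: "Days when oral GVHD medications were held by the prescriber", identified from the medical record, are taken out of the denominator. Missed doses "will be defined as those where no cap was opened on a day medication was prescribed". On reporting: "Adherence will be calculated on a monthly basis and summarized both monthly, and as a 3-month average".

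Section 9.5 sets the monitoring window: "Beginning 2 weeks following the date of discharge from initial HCT hospitalization and for the final duration of the remaining 6 months on study". The initial transplant stay is therefore outside it. The instructions in the patient kit (9.5) tell participants to take every dose from the monitored bottle while on study, and make no exception for hospital stays.

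Later admissions are foreseen. Section 13.7.2 provides that, on "the day after any subsequent hospitalizations, an RA will contact the family by phone to review the MEMS-cap system" and, where relevant, to confirm that the cap is in use. Section 9.6.1 abstracts the drug name, frequency and dose of the prescription. Section 9.6.2 abstracts the "number of and reason for unplanned hospital days".

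No section says how a readmission day is scored, whether an inpatient order counts as a prescribed event, or where inpatient doses come from.

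**The concern.** Under the definition in 11.5.1, a day leaves the denominator only if the prescriber held the drug. A patient who is readmitted, stays on the oral drug and receives it from a source other than the MEMS bottle produces no openings on days that still count as prescribed. Read literally, the rule scores each of those days as missed, although the patient missed nothing.

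The missing-data provisions in 11.7 do not help, because such days enter as observed non-adherence and not as missing values. Randomisation does not remove the problem either, because readmission happens after it.

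Three uses of the rate are exposed:

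- **Aim 1.5.1.** Patients with more readmission would look less adherent, and any difference between arms in readmission would appear as an adherence effect.
- **Cost-consequence ratios (11.5.2).** Hospital days are captured as utilisation, so one readmission could raise the cost side and artificially lower the adherence side of the same ratio.
- **Effect modification (11.6).** Adherence as a modifier would partly stand in for illness severity, while medical covariates are examined separately.

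**Working it through.** The plan gives no expected MEMS rate, sample size or power for this outcome, so there is no figure of its own to reproduce. The check applies the 11.5.1 formula to a 30-day month.

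**Inputs**

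- Formula, exclusion and missed-dose rule: 11.5.1.
- Background adherence of 73% of prescribed doses: section 2.1.1, for illustration only.
- Readmission days *h* and the share *s* of them recorded as held: not in the documents. Assumed ranges are *h* up to 14 days and *s* from 0 to 1.
- No cap openings during the stay: an assumption.

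**Formula.** With true outpatient adherence *a*, the measured monthly rate is a(30 − h)/(30 − h·s). The number of doses per day cancels. If the stay falls in one month of three, the 3-month average is (rate in that month + 2a)/3.

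**Perfect true adherence (a = 100%)**

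| Stay | Month, none held (s = 0) | 3-month average, s = 0 | Month, half held (s = 0.5) | 3-month average, s = 0.5 | All held (s = 1) |
|---|---|---|---|---|---|
| 7 days | 23/30 = 76.7% | (76.7 + 200)/3 = 92.2% | 23/26.5 = 86.8% | 95.6% | 100% |
| 10 days | 20/30 = 66.7% | (66.7 + 200)/3 = 88.9% | 20/25 = 80.0% | 93.3% | 100% |
| 14 days | 16/30 = 53.3% | (53.3 + 200)/3 = 84.4% | 16/23 = 69.6% | 89.9% | 100% |

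**True adherence 73%, s = 0.** The month reads 0.73 × 23/30 = 56.0%, 0.73 × 20/30 = 48.7% and 0.73 × 16/30 = 38.9% for 7, 10 and 14 days. The 3-month averages are 0.73 × 83/90 = 67.3%, 0.73 × 80/90 = 64.9% and 0.73 × 76/90 = 61.6%.

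**Per day and between arms, s = 0.** Each such day lowers the monthly rate by 100/30 = 3.3 points at 100% adherence, or 73/30 = 2.4 points at 73%. If the arms differed by two such days per month, the spurious difference would be 0.73 × 2/30 = 4.9 points to 2/30 = 6.7 points. The documents give no evidence of such a difference, so this only shows the sensitivity.

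**With inpatient days removed from both parts.** The rate is a(30 − h)/(30 − h) = a for any *h* below 30. The corrected rule returns true outpatient adherence whatever the supply arrangement.

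**The case against.** The strongest reply is that the distortion depends on facts the documents do not state. The only text on where doses come from, the kit instructions in 9.5, points to the MEMS bottle throughout. The call after a hospitalization in 13.7.2 fits an interruption in cap use but does not state one. Prescribed events could also be read as the outpatient prescription that participants put in the bottle, in which case inpatient orders never enter the denominator. All of this is fair, and it rules out one tempting inference, that every hospital day counts as a missed dose. The initial stay is outside the window, held days are already removed, and the effect is zero if the bottle is used on the ward.

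A second inference also goes too far: that one 7- to 10-day stay turns a fully adherent patient into a typical 73% one. That is near the truth for a single month with no held days, but the plan also reports a 3-month average, which stays at 89% to 92%.

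A third inference, that the arm comparison is biased, needs an arm difference in readmission that nothing in the documents shows. Without one, the effect between arms is mainly noise.

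The stakes are limited as well. The adherence aim was made exploratory for lack of power and the monitoring was later made optional. Section 11.5.1 specifies no test, and 11.5.2 says its ratios are not a cost-effectiveness threshold.

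None of this supplies the missing rule. Section 11.5.1 states one exclusion and a missed-dose definition without an inpatient exception. Two analysts could score the same readmission differently, and the one who follows the text literally can get a wrong rate.

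**Conclusion.** The concern holds in conditional form. For readmissions after monitoring starts, the definition in 11.5.1 scores a day as non-adherent if the oral drug stays prescribed and the MEMS cap is not opened. The rate then partly measures readmission.

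The size rests on assumed stay lengths, no cap openings in hospital, no days recorded as held, and perfect true adherence. On those terms a stay of 7 to 14 days lowers the month's rate to between 77% and 53%, and the 3-month average to between 92% and 84%. Recording half the days as held reduces the loss. Recording all of them as held, or using the bottle in hospital, removes it.

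The primary HADS analysis is unaffected. The point concerns an exploratory, optional, allogeneic-only outcome and the secondary uses of that rate in 11.5.2 and 11.6. It is worth correcting because the stated rule can give a wrong number and the correction is small.

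**What to change.** In 11.5.1:

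- Define prescribed events as outpatient doses.
- Remove inpatient days, from admission to discharge, from both the numerator and the denominator.
- Report the number of monitorable outpatient days per patient and by arm, beside the monthly rates and the 3-month average.

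Before relying on this, confirm that the monthly medical record abstraction captures admission and discharge dates for planned and unplanned stays. Section 9.6.2 names only a count of unplanned days, and removing days from the numerator needs dates that can be matched to the cap timestamps. If the case report form already holds them, the change is a short addition to the text and some programming. If not, the dates must be added to the abstraction.

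The downside is that months with long admissions rest on fewer days and their rates are less precise. Reporting the monitorable days makes that visible.
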